#### 6.6. Additional Analyses per FDA

Per FDA, the success rates based the following definitions will be summarized by counts and percentages.

FDA Device Success (30 day and all post-procedural intervals):

- Alive and stroke free, with
- Original intended device in place, and
- No additional surgical or interventional procedures related to access or the device since completion of the original procedure (i.e., exit from the cath lab/OR), and
- Intended performance of the device:
- Structural performance: No migration, embolization, detachment, fracture, hemolysis, thrombosis or endocarditis, etc., and
- Hemodynamic performance: Maintenance of relief of insufficiency without producing stenosis (stenosis = MV gradient > 5 mmHg; insufficiency = MR >2+), and
- Absence of para-device complications (e.g., leaflet, chordae or papillary muscle damage; LVOT gradient increase > 10 mmHg; hemodynamically significant ASD requiring closure)

FDA Procedural Success (30 day):

- Device success, and
- No device or procedure related SAE's (life threatening bleed; major vascular or cardiac structural complications requiring unplanned reintervention or surgery; stage 2 or 3 AKI (includes new dialysis); MI or need for PCI/CABG; severe HF or hypotension requiring IV inotrope, ultrafiltration or MCS; prolonged intubation > 48 hours)

FDA Technical Success (at exit from OR):

- Alive, with
- Successful access, delivery and retrieval of the device delivery system, and
- Deployment and correct positioning (including repositioning /recapture if needed) of the single intended device, and
- No need for additional unplanned or emergency surgery or re-intervention related to the device or access procedure

FDA Individual Patient Success (1 year):

FDA Device success and all of the following:

- No re-hospitalizations or re-interventions for the underlying condition (e.g., MR, HF)
- Return to prior living arrangement (or equivalent)
- Improvement vs. baseline in symptoms (e.g., NYHA Class improvement > 1 class)
- Improvement vs. baseline in functional status (e.g., 6MWT improvement > 25 meters)
- Improvement vs. baseline in QoL (e.g., KCCQ improvement > 10)

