7.7 Patients

7.7.1 Inclusion Criteria

The Investigator has the responsibility of screening potential patients to determine if the patients meet all the inclusion criteria. The following are requirements for entry into the study:

1. Signed and dated ethics committee/institutional review board approved study consent form prior to study related procedures
2. Eighteen (18) years of age or older
3. New York Heart Association (NYHA) Functional Class II, III and ambulatory IV heart failure despite optimal medical therapy
4. Candidate for surgical mitral valve repair or replacement as determined by a Heart Team evaluation
5. For patients whose primary mechanism of mitral regurgitation is functional (secondary; FMR) in nature: Elevated BNP > 150 pg/ml or corrected NT-proBNP of 600 pg/ml measured within 90 days prior to enrollment or heart failure hospitalization within 12 months prior to enrollment. These criteria do not apply to patients whose primary mechanism of mitral regurgitation is degenerative (DMR) in nature.
6. Clinically significant mitral regurgitation (3+ to 4+, as defined in Section 18.0) confirmed by transesophageal echocardiography (TEE) within 90 days prior to intervention, **or** transthoracic echocardiography (TTE) within 60 days prior to intervention
7. Left ventricular ejection fraction (LVEF) \geq 20% determined by TTE within 60 days prior to intervention
8. The primary regurgitant jet is non-commissural. If a secondary jet exists, it must be considered clinically insignificant
9. Patient agrees to return for all required post-procedure follow-up visits
10. For patients whose primary mechanism of mitral regurgitation is functional (secondary; FMR) in nature: Six-minute walk test (6MWT) \geq 150 m and \leq 400 m within 60 days prior to intervention. These criteria do not apply to patients whose primary mechanism of mitral regurgitation is degenerative (DMR) in nature.

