
Myocardial Infarction (M-VARC 2015)
	
I. Periprocedural MI (≤ 48 h after the index procedure)
 
A. In patients with normal baseline CK-MB (or cTn): The peak CK-MB measured within 48 h of the procedure rises to $\geq 10\times$ the local laboratory ULN plus new ST-segment elevation or depression of ≥ 1 mm in ≥ 2 contiguous leads (measured 80 ms after the J-point), or to $\geq 5\times$ULN with new pathological Q waves in ≥ 2 contiguous leads or new persistent LBBB, OR in the absence of CK-MB measurements and a normal baseline cTn, a cTn (I or T) level measured within 48 h of the PCI rises to $\geq 70\times$ the local laboratory ULN plus new ST-segment elevation or depression of ≥ 1 mm in ≥ 2 contiguous leads (measured 80 ms after the J-point), or $\geq 35\times$ ULN with new pathological Q waves in ≥ 2 contiguous leads or new persistent LBBB.
 
B. In patients with elevated baseline CK-MB (or cTn): The CK-MB (or cTn) rises by an absolute increment equal to those levels recommended above from the most recent pre-procedure level plus, new ECG changes as described.
 
II. Spontaneous MI (>48 h after the index procedure)
 
Detection of rise and/or fall of cardiac biomarkers (preferably cTn) with at least 1 value above the 99th percentile URL (or ULN in the absence of URL) together with at least 1 of the following:
 
A. Symptoms of ischemia
 
B. ECG changes indicative of new ischemia (new ST-segment or T-wave changes or new LBBB) or new pathological Q waves in ≥ 2 contiguous leads
 
C. Imaging evidence of a new loss of viable myocardium or new wall motion abnormality
 
III. MI associated with sudden, unexpected cardiac death
 
Sudden cardiac death or cardiac arrest, often with symptoms suggestive of myocardial ischemia, and accompanied by presumably new ST-segment elevation or new LBBB and/or evidence of fresh thrombus by coronary angiography and/or at autopsy, but death occurs before blood samples could be obtained or at a time before the appearance of cardiac biomarkers in the blood
 
IV. Pathological findings of an acute myocardial infarction

New York Heart Association Classification (NYHA Class)
	
Class I: Patients with cardiac disease but without resulting limitations of physical activity.
 
Class II: Patients with cardiac disease resulting in slight limitation of physical activity. Patients are comfortable at rest.

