## 6. STATISTICAL ANALYSES

### 6.1. General Considerations

a. For continuous variables, summary statistics will include number of observations, mean, median, standard deviation, minimum, maximum, and 95% confidence intervals (based on normal distribution, unless otherwise specified) per table shells.

b. For categorical variables, summary statistics will include counts, percentages, and 95% Clopper-Pearson confidence intervals per table shells. In general, the denominator for the percentage calculation will be based on total number of subjects with evaluable data for a specified time point unless otherwise specified. Subjects with missing data will be excluded from the denominator.

c. Survival analysis techniques will be used to analyze the time-to-event variables. Summaries will include the number of subjects at risk, number of events, and number of subjects with the event. Subjects without events will be censored at their last known event-free time point. If this event-free time point occurs after the analysis time point, the days to event variable will be set equal to the analysis time point so that the subject will be included in the analysis. For subjects who did not have an event or early withdrawal and have not yet completed the analysis visit, they will be censored at their last information date. Time to first event curves will be constructed using Kaplan-Meier estimates and all post procedure results will be summarized with Kaplan-Meier estimates of event rates. Hazard ratios, confidence interval for the hazard ratios, and p-values may also be presented from a Cox proportional hazards model.

d. Descriptive statistics will be provided at each follow-up assessment, including change from baseline to subsequent time point for selected endpoints. Paired (i.e., subjects with available data at both baseline and respective time point) and unpaired data will be presented separately.

e. If insufficient data are available for summary statistics, then data will be provided only as listings.

f. Unless otherwise specified, descriptive analysis will be performed for all data. Nonparametric techniques may be used if the data does not meet the assumptions of parametric tests.

g. All analyses will be performed using SAS® Software version 9.4 or later (SAS Institute, Inc., Cary, NC).

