#### 6.4. Analyses of Secondary Endpoints

Mitral regurgitation reduction from baseline at 30 days, 6 months, 1 year and annually thereafter will be summarized with counts and percentages.

All-cause mortality rates at 30 days, 6 months, 1 year, and annually thereafter and corresponding 95% confidence intervals will be computed using the Kaplan-Meier algorithm with the standard errors being computed using Greenwood's formula.

Recurrent heart failure hospitalization at 30 days, 6 months, 1 year, and annually thereafter will be analyzed using Poisson regression.

Re-intervention rates for mitral regurgitation at 30 days, 6 months, 1 year and annually thereafter will be summarized with counts and percentages.

Composite of major adverse events (MAE) defined as cardiovascular mortality, stroke, myocardial infarction, new need for renal replacement therapy, severe bleeding and re-intervention for study device related complications at 6 months, 1 year and annually thereafter will be summarized with counts and percentages.

Change from baseline in Left Ventricular End Diastolic Volume (LVEDV), Left Ventricular End Systolic Volume (LVESV), Pulmonary Artery Systolic Pressure, 6MWT distance, BNP/NT-pro-BNP level, effective regurgitant orifice area (EROA) and mitral regurgitant volume at the protocol specified timepoints in the secondary endpoints and clinical outcomes section will be summarized by mean and standard deviation for the PP population. For the analyses of six minute walk test (6MWT), subjects unable to perform the walk due to a medical reason will be considered to have walked an actual distance of zero.

Change from baseline in Quality of Life (QoL) score, as measured by Kansas City Cardiomyopathy Questionnaire (KCCQ), and EQ5D at 30 days, 6 months and 1 year and annually thereafter will be

summarized by mean and standard deviation. Patients that are missing a baseline or follow up values will be excluded from the analysis.

Change from baseline in NYHA Functional Classification at 6 months, 1 year and annually thereafter will be presented as shift from baseline for each of the pre-specified follow-up periods. Subjects that are missing a baseline or follow-up values will be excluded from the paired analysis.

Change from baseline in tricuspid regurgitation at 6 months, 1 year and annually thereafter will be summarized with counts and percentages.

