## **10. TABLES, LISTINGS, and GRAPHS**

The tables, listings, and graphs shells will be provided in a separate document, namely the second part of the SAP.

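### The only NYHA threshold printed for FDA Individual Patient Success in SAP 6.6, if applied as printed, cannot be met by eligible class II patients and caps the 1-year rate

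*SAP*

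**What the plan says.** SAP 6.6 (Additional Analyses per FDA) lists success definitions that will be reported as counts and percentages. FDA Individual Patient Success at 1 year requires "FDA Device success and all of the following". The list covers rehospitalization and re-intervention, living arrangement, symptoms, functional status and quality of life. The symptom item reads "Improvement vs. baseline in symptoms (e.g., NYHA Class improvement > 1 class", with the bracket closing after that phrase. The functional and quality-of-life items are also illustrated only by examples (6MWT > 25 meters, KCCQ > 10).

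Protocol 7.7.1, criterion 3, admits "New York Heart Association (NYHA) Functional Class II, III and ambulatory IV heart failure despite optimal medical therapy". Protocol 17 places the top of the scale at "Class I: Patients with cardiac disease but without resulting limitations of physical activity".

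SAP 6.1(b) sets the default denominator: "the denominator for the percentage calculation will be based on total number of subjects with evaluable data for a specified time point". SAP 6.6 does not depart from it. Elsewhere the SAP treats NYHA only descriptively: under SAP 6.4 the change "will be presented as shift from baseline for each of the pre-specified follow-up periods". SAP 7.9 merely lists NYHA among the clinical results, and SAP 8 does not mention it. No responder threshold for NYHA appears anywhere else in the SAP text.

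**The concern.** The one threshold on the page does not fit the eligible population. NYHA class takes whole-number values, so an improvement of more than one class means at least two. A class II patient who becomes free of limitation has improved as far as the scale allows and would still be scored a failure on this item. Because every item is required, that patient would also fail the composite.

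The 1-year rate would then partly measure baseline case mix instead of outcome. A cohort with more class II patients would have a lower attainable rate however well the device worked in them. The study objectives include guiding later study designs, and a rate with a hidden ceiling is a poor guide. The NYHA shift table shows movement from class II to class I, but it cannot rebuild a composite that also depends on device success, rehospitalization, 6MWT and KCCQ.

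**Working it through.** The plan gives no expected rate for this endpoint, so there is no figure to reproduce. The check lists the possible NYHA changes and derives the resulting bound.

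**Inputs.** Eligible baseline classes: II, III and ambulatory IV (Protocol 7.7.1). Best class: I (Protocol 17). Combination rule: all components required (SAP 6.6). Denominator: patients with evaluable data at the time point (SAP 6.1(b)). Primary-cohort analysis population: 60 (Protocol 7.1, SAP 2.2). The class II share q is not in the documents and is assumed.

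**Step 1. Largest possible improvement = baseline class − 1.**

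| Baseline | Largest improvement | Meets > 1 class by reaching | Meets ≥ 1 class by reaching |
|---|---|---|---|
| II | 2 − 1 = 1 | none | I |
| III | 3 − 1 = 2 | I | I or II |
| IV | 4 − 1 = 3 | I or II | I, II or III |

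**Step 2. Bound on the composite.** Under > 1 class, the probability of success given baseline class II is 0. For the remaining share, 1 − q, it is at most 1. Hence

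rate ≤ q × 0 + (1 − q) × 1 = 1 − q.

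Under ≥ 1 class, every eligible class can meet the NYHA item, so the item imposes no such bound.

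**Step 3. Range over assumed q.** The last column is an illustration that takes all 60 patients as evaluable at 1 year.

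| Assumed q | Ceiling 1 − q | Most successes possible out of 60 |
|---|---|---|
| 20% | 80% | 60 − 12 = 48 |
| 30% | 70% | 60 − 18 = 42 |
| 40% | 60% | 60 − 24 = 36 |
| 50% | 50% | 60 − 30 = 30 |

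The percentage ceiling depends on q alone, not on the number analysed. If no class II patients are analysed (q = 0), there is no ceiling.

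**The case against.** The strongest reply is that the criterion itself is improvement in symptoms, which a class II patient meets by reaching class I, and that the threshold is only an example. This stands in part: the ceiling exists only if the example is coded as the rule. But it is the only threshold printed, and nothing else in the SAP text points to another.

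Second, the symbol may be a reading artefact, with an underlined > having lost its underline. The SAP text does keep a less-than-or-equal sign in 3.1 and 6.3, and the protocol keeps ≥ in 7.7.1, but the SAP text shows no ≥ for comparison. Loss of the underline is therefore possible and not shown. A reader might infer a definite sponsor error; the documents do not support that.

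Third, a fixed rule may stand in the table shells. SAP 6.1(b) says that "summary statistics will include counts, percentages, and 95% Clopper-Pearson confidence intervals per table shells", and SAP 10 says "The tables, listings, and graphs shells will be provided in a separate document, namely the second part of the SAP". That document is not available here, so it would be too strong to say that no operative rule exists anywhere.

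Fourth, the section reports definitions attributed to FDA, and a demanding composite may be intended. The fix allows for this.

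**Conclusion.** The point holds conditionally and is minor. If improvement by more than one class is applied as printed, class II patients cannot reach FDA Individual Patient Success, and the 1-year rate cannot exceed 1 − q: 80% to 50% for assumed q of 20% to 50%. Given the threshold, this follows from the scale and the eligibility rule. What is uncertain is whether the threshold will be used in that form, and what q will be.

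Two stronger readings should be resisted. One is that 12 to 30 of 60 successes would be lost. Those are the class II patients who could not succeed under the printed threshold. Some would fail device success, rehospitalization, 6MWT or KCCQ in any case, so the documents support an upper limit on the rate and not a count of losses. The other is that the trial's main conclusions are at risk. The rate is an additional descriptive summary with no hypothesis or performance goal attached, and no primary or secondary endpoint uses it.

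**What to change.** Confirm the symbol in the original SAP, and check the table shells and the FDA definition at the same time. Then replace the example in SAP 6.6 with one fixed rule: NYHA improvement of ≥ 1 class from baseline. If > 1 class is confirmed as FDA's definition, keep it, state in the SAP and beside the result that class II patients cannot meet it, and report the rate with ≥ 1 class alongside. In the same edit, fix the 6MWT and KCCQ thresholds as rules and say whether each is strict or inclusive.

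The cost is a line of SAP text and at most one extra descriptive rate. No new data are needed, since Protocol Table 1 already schedules NYHA class at baseline and 1 year.

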## 7. LIST OF KEY VARIABLES

The following parameters will be summarized. Other parameters may be added as deemed necessary.

### 7.1. Subject Enrollment and Disposition

Subject disposition will be summarized in a table. A subject level listing will also be provided.

### 7.2. Demographics and Baseline Characteristics

- Age (in years)
- Gender
- Body Mass Index (BMI)
- Tobacco use
- Logistic EuroSCORE I (%)
- EuroSCORE II (%)

- STS Mortality Score (%)
- NYHA Class
- 6 Minute Walk Test – Total distance of walk (m)

### 7.3. Medical History

- Cardiovascular Risk Factors
  - Angina
  - Aortic Aneurysm
  - Aortic Valve Disease
  - Arrhythmia and Conduction Defects
  - Atrial Septal Defect (ASD)
  - Cardiomyopathy
  - Carotid Artery Stenosis
  - Cardiogenic Shock
  - Coronary Artery Disease
  - Deep Vein Thrombosis (DVT)
  - Endocarditis
  - Heart Failure
  - Hypertension
  - Lower Extremity Edema > 2+
  - Myocardial Infarction (MI)
  - Mitral Valve Disease
  - Pericarditis
  - Peripheral Vascular Disease
  - Porcelain Aorta
  - Pulmonary Embolism (PE)
  - Pulmonic Valve Disease
  - Rheumatic Heart Disease
  - Syncope
  - Thromboembolic Disease
  - Tricuspid Valve Disease
  - Ventricle Septal Defect (VSD)
  - Stroke or Cerebrovascular Accident (CVA)
  - Transient Ischaemic Attack (TIA)
- Non-Cardiovascular Risk Factors
  - Amyotrophic Lateral Sclerosis (ALS)
  - Chronic Headache or Migraine
  - Dementia (including Alzheimer's)
  - Infectious (including Guillian-Barre Syndrome)
  - Multiple Sclerosis
  - Parkinson's
  - Seizure Disorder (including Epilepsy)
  - Spinal Cord Injury
  - Traumatic Brain Injury (TBI)

- Asthma
- Bronchitis
- Chronic Obstructive Pulmonary Disease (COPD)
- In-home oxygen use
- Chronic lung disease
- Emphysema
- Lung Infection (i.e. Pneumonia or TB)
- Pulmonary Hypertension
- Pulmonary Edema
- Pulmonary Fibrosis
- Pulmonary Embolism
- Cor Pulmonale
- Sleep Apnea
- Other pulmonary disease
- Diabetes (Type I, Type II)
- Dyslipidemia
- Other endocrine conditions
- Renal Disease
- Gastrointestinal Bleeding
- Variceal bleeding
- Crohn's Disease
- Ulcerative Colitis
- Cirrhosis
- Other gastrointestinal conditions
- Chronic Urinary Tract Infections
- Disease of the Prostate
- Cancer/Malignancy
- Coagulopathy (including haemophilia and factor deficiencies)
- Chronic Anemia
- Thrombocytopenia
- HIV/AIDS
- Subject currently taking immunosuppressants?
- Autoimmune Disorder
- Marfan's Syndrome
- Hostile Chest/ Chest Deformities
- Prior radiation treatment that precludes an open chest procedure

#### 7.4. Prior Interventions or Surgeries

- Prior Cardiovascular Interventions or Surgeries
  - Pacemaker or ICD implant
  - PCI/Stent
  - Coronary Artery Bypass Graft (CABG)
  - Electrophysiological procedures (EP procedures)
  - Previous valve replacement or repair
  - Carotid endarterectomy / Carotid stent

- Cardiac Devices
- Atrial Septal Defect (ASD) Repair
- Ventricular Septal Defect (VSD) Repair
- Cardiac Transplant
- Peripheral Vascular Intervention
- Implanted Inferior Vena Cava (IVC) Filter

#### 7.5. Procedure Information

- Type of anesthesia (Conscious sedation, General anesthesia)
- Access side through which device advanced (Left femoral vein, Right femoral vein)
- Total operative lab duration (min)
- Skin incision to Femoral vein access closure time (min)
- Femoral vein access closure method (Percutaneous closure device, Surgical closure of cut-down, Other)
- Cardiopulmonary bypass (Yes, No)
- Fluoroscopy duration (min)
- Volume of contrast used (ml)
- Pre-implant echocardiographic mitral regurgitation assessment (Site-Reported)
- Post-implant echocardiographic mitral regurgitation assessment (Site-Reported)
- Implant hospitalization length of stay (days)

#### 7.6. Device Usage and Malfunction

- Total number of study devices implanted
- Reason for additional implant(s) of study devices
- Number of non-study devices used
- Name of non-study device

#### 7.7. Safety Variables

Number of unique subjects who experienced adverse events will be reported by AE category for each analysis cohort.

Events will be adjudicated by the CEC according to the CEC Charter. The CEC adjudicated adverse events will be summarized by KM estimate and/or binary proportions.

Number of unique subjects who experienced heart failure rehospitalization will be reported.

#### 7.8. Primary Performance Endpoints

- Device Success (Per Device Analysis)
- Procedural Success (Per Patient Analysis)
- Clinical Success (Per Patient Analysis)

#### 7.9. Clinical Results

- New York Heart Association (NYHA) Functional Class
- Six Minute Walk Test (6MWT)
- Kansas City Cardiomyopathy Questionnaire (KCCQ) Scores
- EQ5D Scores

#### 7.10. Transthoracic Echocardiogram (TTE) & Transesophageal Echocardiogram (TEE) Parameters

##### Transthoracic Echocardiogram (TTE) Parameters

- Mitral annular calcification (Baseline only)
- MR Mechanism (Baseline only)
- LVEDD
- LVESD
- LVEDV
- LVESV
- Ejection Fraction (EF)
- Pericardial effusion
- Mitral Valve Area
- EROA (MR effective regurgitant orifice area)
- Regurgitant Volume
- Regurgitant Fraction
- MR Severity

##### Transesophageal Echocardiogram (TEE) Parameters

- Mitral annular calcification (Baseline only)
- MR Mechanism (Baseline only)
- MR Severity

## **8. CHANGES FROM PROTOCOL SPECIFIED ANALYSES**

Definition of Implanted population and related analysis were not in the protocol. They were added to the SAP due to the clinically meaningfulness of this population.

